To conduct a pilot feasibility RCT among up to 48 women, either diagnosed with GDM and referred to the High Risk Obstetric Consultants (HiROC) at the University of Tennessee Medical Center Knoxville (UTMC), or at risk for GDM (e.g., failed the 50g, 1-hr screening test) and managed by one of the clinics listed in Section J. The RCT will compare a physical activity (behavior change) intervention (i.e., walking/stepping in place) versus a general wellness intervention (i.e., health education focusing on immunizations, contraceptive options following delivery, etc.) on PA levels, maternal glycemic profile in the third trimester, and infant size and anthropometrics (i.e., weight, length, head, abdominal and upper mid-arm circumference, and skinfolds at the flank, thigh, triceps, bicep and subscapular).

It is hypothesized that the PA intervention will increase PA levels during pregnancy, and improve maternal glycemic profile in the third trimester and infant anthropometric measures at birth. The exploratory hypothesis is that improvements in third trimester glycemic profile mediate the effect of pregnancy PA on the infant anthropometric measures.

C. Study Staff

Student research assistants working on the study (i.e., recruitment, conducting intervention sessions and data assessment visits) will be trained and overseen by Drs. [name] and [name]. All will remain up to date on required IRB trainings and approvals (e.g., CITI trainings and UTMC outside learner approval) for the duration of their work on the study.

D. Usual Care

Usual care at HiROC for women with GDM includes bimonthly to weekly in-person appointments, depending on the patients' needs and adherence to the diabetes

educators' recommendations, to monitor their capillary glucose levels, provide counseling on diet, and prescribe or adjust medications, as needed. PA is usually encouraged at the first GDM appointment, but is not directly prescribed, further discussed or typically tracked in conjunction with usual clinical care. Women at risk for GDM (i.e., who fail the screening but not the diagnostic test), are not seen by HiROC for diabetes education.

E. Data Assessment Overview: The Project Wellness Study Visits

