Surveys (e.g., demographic, health behaviors, medical history, dietary intake) will be administered at baseline (initiated < 30 weeks gestation, Study Visit 1) and at follow-up (initiated < 36 weeks gestation, Study Visit 2); see Table 1 for the variables to be assessed and timing of their assessments. PA will be objectively measured at baseline and follow-up with ActiGraph physical activity monitors (PAMs, i.e., the CentrePoint Insight Watch) worn continuously for 7 days on the dominant wrist. Continuous glucose monitors (CGM) will be worn continuously for 7 days on the participants' non-dominant upper arm (posteriorly located) at Study Visits 1 and 2 to assess maternal glycemic profile (i.e., DEXCOM G6 devices, participants will be blinded to their CGM data). Infant outcomes [i.e., weight; length; head, abdominal and upper mid-arm circumferences; and skinfolds at four sites (flank, thigh, triceps, bicep and subscapular skinfolds)]^{18,64} will be assessed by study staff within 4 days of birth (i.e., the optional delivery visit).

Participants will be randomized to the STEP Up intervention or the Next Steps intervention (described in Section R) once they have successfully completed all of the data assessments for Study Visit 1 (described in Section L). Intervention staff will inform the participants of their program assignment (i.e., STEP Up or Next Steps) and schedule the first intervention session. All intervention sessions will be conducted remotely (i.e., via phone and/or video chat).

Study visits will occur either remotely (i.e., via phone and/or video chat) or take place in private rooms at the UT Medical Center [e.g., a private office or exam room in the High

Risk Obstetrical Consultants (HiROC) clinic or Preston Medical Library; and Labor and Delivery or the Mother/Baby Units on 3 West, 3 East, and 4 West for the delivery visit].

F. Incentives

Participants will receive payments in the amount of: \$80 for Study Visit 1, \$100 for Study Visit 2, and \$100 for the delivery visit (i.e., \$280 total). Incentive payments will be Walmart gift cards distributed either in person, by mail, or dropped off at the participants home upon completion of all of the data assessment elements associated with that Visit. If a gift card is sent by mail and not received, a replacement will be dropped off at the participants home.

G. Parking

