Participants will receive vouchers to cover the cost of parking at the Medical Center for any in-person Study activities (described in Sections L, N and O; one voucher will be provided at the delivery visit).

Table 1. Variables to be measured at the study visits.

	Medical Chart	Physician Screen/ Study Visit 1 (≤ 30 weeks)	Study Visit 2 (≤ 36 weeks)	Delivery Visit	3-month Infant Follow up Visit	6-month Infant Follow up Visit	9-month Infant Follow up Visit	1-year Infant Follow up Visit
Demographics								
Age		X						
Race-ethnicity		X						
Working status		X	X		X	X	X	X
SES, Marital status, Insurance status		X				X		
Smoking, Alcohol, Illegal drugs		X						
Sleep		X	X					
Biomedical								
Height	X	X						
Weight (pre-pregnancy, during pregnancy and postpartum)	X	X	X		X	X	X	X
Medical history		X			X	X	X	X
Medication use	X	X	X					
Pregnancy history/outcomes	X				X			

Prior use of and intentions for contraceptives		X	X					
Contraception initiation and use following delivery	X				X	X	X	X
Vaccination (flu and Tdap) perceptions and intentions for vaccination	X	X	X		X	X	X	X
Capillary glucose values (i.e., 7 days of values recorded in purple booklets, for women with GDM only)		X	X					
Continuous Glucose Monitor (i.e., 7 days)		X	X					
Infant Anthropometrics				X (optional)	X	X	X	X
Infant feeding and immunizations					X	X	X	X
Actigraph Physical Activity Monitor		X	X		X	X	X	X
Food Frequency Questionnaire (FFQ)		X	X					

Physical activity questionnaires		X	X		X	X	X	X
Stage of change for Physical Activity		X	X					
Diabetes Risk Perception & Family History of Diabetes		X						
Self-efficacy for Physical Activity		X	X		X	X	X	X
Social support for Physical Activity		X	X		X	X	X	X
Symptoms of Depression		X	X					
Adverse events			X					
Acceptance of interventions			X					

H. Advertising the study

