Participants may experience skin irritation or redness around the continuous glucose monitor device's adhesive patch, and there is the potential risk of infection. They will be instructed to avoid placing the device near tattoos, scar tissue, and boney areas.

If the participant is conducting the Study Visit in-person, then research staff will apply the CGM transmitter and set up the CGM receiver for them. Applying the CGM transmitter involves using a device-specific applicator to affix an adhesive casing to the back of the upper arm, and then placing the CGM transmitter into this casing so that it

remains continuously on the body. If it is a remote visit, a Zoom or telephone meeting will be scheduled so that research staff may verbally assist the participant and their adult family member/partner who will help them apply the CGM transmitter. For the remote visits, participants and the person helping them apply the CGM transmitter will be instructed to watch the YouTube video (link above) on application. First, an alcohol prep pad will disinfect the upper posterior portion of the participant's non-dominant arm, then research staff or the person helping them at home will apply the adhesive casing (i.e., place the applicator on upper arm, and push the orange button) and then insert the CGM transmitter into the casing. Next, research staff will either set up the CGM receiver, or walk the participant through setting up the receiver by inputting the serial numbers included on the CGM transmitter packaging.

At the end of the CGM assessment, participants, either themselves or with assistance, will peel off and remove the casing/CGM transmitter from their arm. The participants will also disable the CGM receiver once the transmitter has been removed. Only the CGM receiver and charger will be returned to study staff (i.e., the transmitter and its adhesive casing may be discarded).

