Staff will remind the participant of the scheduled day/time of her Study Visit 2 either during an intervention session or by text message (see Section R for a description of the interventions). Study visit 2 may occur remotely, via Zoom, or at UTMC. If it is a remote visit, all materials will have been either mailed ahead of time or dropped off at the participants' home. First, the women's weight will be measured by study staff and the 'in-person' survey completed (e.g., to collect information on adverse events). If it is a remote visit, a scale will be left with at the home with her other study materials, and a weight measurement taken during/soon after the Zoom session. Weight will also be obtained from the medical record. Second, study staff will review the PAM data assessment protocol (e.g., they will be asked to wear the device continuously for 7 days on their dominant wrist, but if that is not possible, they are to record the days/times of device removal in a diary log) and give the women her PAM and PAM diary log. Third, study staff will give the participant a Study Visit 2 at home survey and Food Frequency Questionnaire (FFQ) to take home, plus a number 2 pencil for the FFQ. Forth, the medical release form for their infants' data will be reviewed.

In addition, the continuous glucose monitor will be applied to the participant.

If the participant has GDM, copies of her purple HiROC capillary glucose record sheets will be obtained. Participants will return their Study Visit 2 materials to study staff by leaving them with the HiROC receptionists (e.g., if they have a prenatal care

appointment already scheduled), mailing them (i.e., prepaid FedEx mailers with the study's address will be provided), or arranging for study staff to pick them up (the later preferred).

O. Newborn Infant Measurements, the Delivery Visit

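### No adverse event item is visible after the survey that opens Study Visit 2, although the second glucose monitor wear and any late STEP Up sessions come later

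*Protocol*

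**What the plan says.** The schedule of assessments (Protocol, Table 1) has a row "Adverse events" with a single mark, under Study Visit 2. The row is empty for the medical chart, Study Visit 1, the delivery visit and all four infant follow-up visits.

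Section N gives the order of Study Visit 2. Weight and the in-person "survey completed (e.g., to collect information on adverse events" come first. The activity monitor, the at-home survey and food questionnaire, and the infant release form follow, and the glucose monitor is applied at the same visit. Section E sets the wear time: "Continuous glucose monitors (CGM) will be worn continuously for 7 days on the" upper arm, at both study visits. Section L names the device risks: "Participants may experience skin irritation or redness around the continuous glucose monitor" patch, and possible infection.

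Table 1 and the heading of Section N place the visit at or before 36 weeks. Section E has it "initiated < 36 weeks gestation, Study Visit 2". Section P offers STEP Up participants optional, roughly weekly maintenance sessions past 36 weeks and up to delivery. Next Steps has no such phase.

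The SAP text available describes the activity and neonatal comparisons and gives no adverse event summary.

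**The concern.** An adverse event question can only cover what has already happened. Here the one visible item is asked when the second sensor is about to be worn and while STEP Up walking may continue for weeks. A pilot is where a team learns what its procedures and intervention cause before a larger trial. If the schedule is followed as it reads, skin reactions at the second wear and minor events in the last weeks of pregnancy have no visible point of collection. Maintenance contacts exist in one arm only, so events that women volunteer late could also be heard more often in STEP Up than in Next Steps. At stake is the completeness and symmetry of the safety record, not the outcome comparisons.

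**Working it through.** The plan gives no figure to reproduce. The check sets the sections side by side and dates the gap.

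**Inputs from the protocol**
- One adverse event mark, at Study Visit 2 (Table 1), in the survey completed first (Section N).
- Visit 2 at or before 36 weeks (Table 1, Section N); before 36 weeks in Section E.
- Sensor worn for 7 days from the visit (Sections E and N).
- First intervention session by 31w6d; four more, about weekly, by 36w6d (Section P).
- Newborn measurements "within 4 days of birth (i.e., the optional delivery visit" in Section E).

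**Assumptions, not in the documents**
- Delivery between 37w0d and 41w0d.
- The 3-month visit falls 91 days after birth.

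**Step 1. Order.** Section N does not number the sensor step. A 7-day wear that begins at the visit must still run past a survey completed first at that visit, so the whole second wear follows the item. The first wear precedes it for every randomized woman, because Section L makes a completed wear a condition of randomization.

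**Step 2. Gap to delivery.** Gestational day = 7 × weeks + days. Gap = delivery day − visit day. 37w0d = 259 and 41w0d = 287.

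| Visit 2 | Day | Delivery 37w0d | Delivery 41w0d |
|---|---|---|---|
| 36w0d | 252 | 259 − 252 = 7 days | 287 − 252 = 35 days |
| 35w6d (last day under Section E) | 251 | 8 days | 36 days |
| 36w6d (if ≤ 36 weeks is read to allow it) | 258 | 1 day | 29 days |

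An earlier visit lengthens the gap day for day. In the shortest case for a 36w0d visit, the wear fills the gap: 252 + 7 = 259.

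**Step 3. Core sessions.** With the latest first session, 31w6d = day 223, and four weekly sessions, the last falls on day 223 + 4 × 7 = 251, or 35w6d. For a visit at 36w0d, only rescheduled core sessions would follow the item. For a visit before 35w6d, the last core session could follow it too.

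**Step 4. Recall under the remedy.** Recall = gap + time from birth to the question, for Visit 2 between 36w0d and 36w6d.
- Delivery visit, 0 to 4 days after birth: 1 + 0 = 1 day to 35 + 4 = 39 days.
- 3-month visit: 1 + 91 = 92 days (13.1 weeks) to 35 + 91 = 126 days (18.0 weeks).

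**The case against.** **The mark may cover the whole visit.** Section L counts the surveys, device wear and diary log as elements of Study Visit 1. By the same logic, the Table 1 mark could take in the Visit 2 at-home survey, which is returned later. Section N also mentions adverse events only as an example of what the in-person survey collects. This stands as a limit. A reader might infer that the trial asks about adverse events only once. The documents do not support that, because the at-home survey content is not shown and the consent pages and part of the SAP were not available. What can be said is that no later item is visible in Table 1 or Sections N to P.

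**Other routes exist.** Staff search the admission system and the labor and delivery board (Section O). "Pregnancy history/outcomes" come from the chart and at 3 months, and medical history is taken at 3 to 12 months (Table 1). "Usual care at HiROC for women with GDM includes bimonthly to weekly in-person appointments" (Section D). Women in maintenance sessions speak to staff about weekly. This largely stands for serious events, so a reader who infers that safety goes unobserved after Visit 2 goes too far. The routes are partial for minor events. Women who fail only the screening test are not seen at HiROC for diabetes education, and the at-risk stratum is planned as half the sample (Sections D and M). Maintenance contact is informal and confined to one arm.

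**Days are not exposure.** The gap counts calendar time. Uptake of maintenance sessions is not stated and may be zero. In Next Steps, the only study exposure shown after Visit 2, apart from a late core session, is one sensor wear. This stands, and it is why the point has low priority.

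**Conclusion.** The point holds as a minor gap in safety ascertainment. The one visible adverse event item precedes the second sensor wear and any STEP Up maintenance sessions. For a visit at 36w0d, 7 to 35 days before delivery have no visible item. That range rests on the assumed delivery window and moves by a day or a few with the reading of the 36-week limit.

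What can be missed is mainly minor: sensor-site reactions at the second wear and events in late pregnancy that lead to no admission or chart entry. A reader might go on to infer bias in the activity, glucose or infant comparisons. Nothing in the documents supports that, since none of those outcomes depends on when adverse events are asked about. The finding would fall away for the sensor wear if the Visit 2 at-home survey already has such an item and is completed after the wear.

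**What to change.** In both arms:

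1. Add an item on sensor-site skin reactions and other adverse events to the Visit 2 materials returned after the wear, or ask it when staff collect them. The at-home survey is the natural place. A line on the returned log would also work, though that log belongs to the wrist activity monitor.
2. Add an adverse event mark to the medical chart column of Table 1, and ask one item at the delivery visit, or at 3 months if that visit is declined or canceled.
3. Tabulate events descriptively by arm, for randomization to Visit 2 and for Visit 2 to delivery.

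The cost is one item in the returned materials, one chart field, one later item and one table, all at contacts already planned.

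There are two downsides. Recall is 1 to 39 days at the delivery visit but about 13 to 18 weeks if the question is asked only at 3 months, so minor events would be under-reported; the returned item and the chart field limit this. The first wear would still be covered by recall at Visit 2, so counts from the two wears should not be compared directly.

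The SAP is dated 8/8/2023. If data collection had ended by then, the new items could serve only a later trial. Chart abstraction, the table and a stated limit on ascertainment may still be possible in this one.

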On the Study Visit 1 in-person survey, participants will be asked if they are interested in participating in the optional delivery visit. If so, they will be asked to provide the names and telephone numbers of 1-2 individuals who plan to be with them at the delivery and to give study staff permission to contact those individuals to help schedule the newborn infant measurements. Participants will be asked to update this information, if it has changed, at Study Visit 2 in-person survey. Study staff will check in with those individuals by text every few days around the woman's estimated delivery date/C-section date to schedule the newborn infant measurements, ideally before she is discharged.

Study staff will also distribute delivery visit reminder cards at Study Visits 1 and 2 that contain the telephone number to call or text once they go into labor; participants will be instructed to keep this reminder card in their hospital bags.

Study staff will also remain in contact with the UTMC staff in labor and delivery so they are aware that the patient is a study participant and will need newborn infant measurements. Study staff will additionally search the Medical Center's electronic admission system and the labor and delivery patient board for study participants as they near delivery. UTMC staff in labor and delivery and the Mother/Baby Units will also help facilitate scheduling the delivery visit to obtain the newborn measurements.

Newborn measurements will not be taken if the baby is admitted to Neonatal Intensive Care and is critically ill. Measurements will take place only at UTMC or the participants' homes.

First, study staff will weigh the baby (using a portable study scale). Second, study staff will measure the length of the infants (i.e., recumbent length with a portable infantometer). Third, study staff will measure the infant's head, abdominal and arm circumferences (i.e., using a tape measure). Forth, study staff will measure flank, thigh, triceps, bicep and subscapular skinfolds with calipers to assess body composition. The mother can hold the infant during the circumference and skin folds measurements. Although there is no risk of harm from these measures, the baby may briefly experience a very mild discomfort resulting from the light pinch of skin with the caliper (this pinching sensation is about as uncomfortable as if one were to lightly take a pinch of skin between the fingers).

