Due to COVID-19, the Delivery Visit may potentially be canceled.

P. Interventions

The primary goal of the PA intervention is to achieve at least 30 minutes per day of walking/stepping in place. The secondary goal is to use a physical activity tracker to log and track their walking/stepping in place, and to get at least 3,000 steps during their 30 minutes of walking/stepping. The STEP Up intervention will offer a FitBit Charge 3; the devices will be managed by Fitabase so that both the participant and the interventionists will be able to view her Activity Log (i.e., the Fitbit's record of minutes spent walking/stepping and the number of steps obtained during those minutes), and will thus encourage the use of that device. Women randomized to the PA intervention will have an initial video chat (i.e., Zoom) counseling session to discuss exercising safely and exercising safely during pregnancy, go over the STEP Up program goals, set a walking/stepping goal for the following week, and receive and review use of the Fitbit to track progress towards their goal. They will then participate in 4 telephone/video chat sessions to discuss progress towards their walking/stepping goals and receive behavior change counseling to maintain and increase their walking/stepping (i.e., approximately 1 telephone session per week). They will be offered optional maintenance sessions

through delivery, as requested (i.e., approximately weekly). If the participant does not have internet access, the intervention will be delivered entirely by telephone.

Women randomized to the 'Next Steps' intervention will receive information on mom and baby wellness that is unrelated to physical activity, diet, metabolism, or weight (e.g., her own immunization status during pregnancy and encouragement to immunize her baby on schedule, infant car seats & safety checks, contraceptive options and a contraceptive plan), delivered in 5 telephone/video chat sessions (identical to the STEP Up intervention described above) in order to control for contact time. As such, the trial is called Project Wellness and it will be advertised that all study participants will work with a lifestyle coach on wellness.

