**Statistical Analysis Plan date:**

8/8/2023

Analyses will be intention to treat. Mean daily minutes spent in walk/run activity and MVPA (i.e., device-based measures), as well as mean MET hours per week in the sports and exercise domain overall and just walking and jogging (i.e., questionnaire-based measures) will be compared between groups with Proc Mixed in SAS 9.4. All models will be adjusted for GGI vs. GDM status. Models of the device-based measures will include repeated statements for observation day number, by study visit. The model for total MVPA will include additional adjustment for device wear-time (i.e., by day and study visit). Models for the questionnaire-based measures will include repeated statements for study visit. For the neonatal outcomes, PA intervention verse control group differences will be examined in Proc Mixed, adjusting for GGI vs. GDM status.

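### Infant weight comes only from an optional, restricted delivery visit; chart birth weight for all obtainable randomised pairs would be a cheap improvement

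*Protocol*

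**What the plan says.** **Source of infant weight.** Protocol Section E lists weight first among the infant outcomes, which "will be assessed by study staff within 4 days of birth (i.e., the optional delivery visit". In Section O, "study staff will weigh the baby (using a portable study scale". In Table 1 the infant anthropometrics row is marked optional at the delivery visit and has no mark under Medical Chart.

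**Who may go unmeasured.** At Study Visit 1, "participants will be asked if they are interested in participating in the optional delivery visit". Section O adds three restrictions. The first concerns place: "Measurements will take place only at UTMC or the participants' homes". The second concerns illness in the infant: "Newborn measurements will not be taken if the baby is admitted to Neonatal Intensive Care and is critically ill". The third concerns the pandemic: "Due to COVID-19, the Delivery Visit may potentially be canceled".

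**Hints of a chart route.** Table 1 marks "Pregnancy history/outcomes" under Medical Chart and at the 3-month visit. Section N has a release form for the infant's medical data reviewed at Study Visit 2. Neither place names birth weight. For the mother the protocol is explicit: Sections L and N say her weight is also taken from the medical record. There is no matching sentence for the infant.

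**Analysis.** The SAP states intention to treat and then says: "For the neonatal outcomes, PA intervention verse control group differences will be examined in Proc Mixed, adjusting for GGI vs. GDM status". In the text available it does not list those outcomes, name their source or say how unmeasured infants are handled. Part of the SAP file was not available, so this statement covers only its analysis paragraph.

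**The concern.** Infant anthropometrics at birth are part of the stated hypothesis (Section B), and Section A names large-for-gestational-age birth and macrosomia among the precursors of childhood obesity. If the visit is the only source of weight, randomised women whose infants are not measured drop out of that comparison.

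Two kinds of loss need to be kept apart. Declining the visit at Study Visit 1 comes before randomisation (Sections L and M), so allocation cannot cause it; it costs precision and narrows the population. Later non-completion, delivery elsewhere without a home visit, and the intensive-care rule all act after randomisation and could differ by arm. One possible route is in the protocol itself: Section P offers only the physical activity arm roughly weekly sessions through to delivery, so staff contact may differ just when the visit has to be arranged.

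Weight is the one planned newborn measure for which the documents hint at a second source. A recorded birth weight would also fix the age at weighing, which the visit leaves open over 4 days.

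**Working it through.** The plan gives no power, SD, completion rate or chart-coverage rate, so there is no figure of its own to reproduce. What follows is for scale only.

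**Inputs.** Section M plans for about 36 randomised with equal arms, so 18 per arm. The SAP model has an intercept, arm and GGI vs. GDM status, which leaves N - 3 degrees of freedom. Numbers of infants below 36 are assumptions.

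**Step 1: what the model uses.** Weight at birth has one value per infant and no baseline value. The SAP describes repeated statements for the activity measures but none for the neonatal outcomes. A record with no weight therefore contributes nothing to the Proc Mixed fit, and the comparison is of measured infants.

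**Step 2: precision.** In SD units with equal arms, half-width of the 95% CI = t(0.975, N - 3) × √(4/N). For N = 36 this is 2.035 × 0.333 = 0.678.

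| Infants with a weight | Half-width (SD) | Relative to 36 |
|---|---|---|
| 36 | 0.678 | 1.00 |
| 34 | 0.700 | 1.03 |
| 32 | 0.723 | 1.07 |
| 29 | 0.763 | 1.13 |
| 22 | 0.892 | 1.32 |

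**Step 3: how much noisier may chart weight be?** Break-even extra error variance, as a share of between-infant variance, = (half-width at visit N ÷ half-width at chart N)² - 1. For 36 chart weights against 29 visit weights: (0.763 ÷ 0.678)² - 1 = 0.27.

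| Visit N | Chart N = 36 | Chart N = 34 |
|---|---|---|
| 34 | 6% | no gain |
| 32 | 14% | 7% |
| 29 | 27% | 19% |
| 22 | 73% | 63% |

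If chart coverage is no higher than visit completion, chart weight brings no precision gain.

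**Step 4: possible bias.** If m more infants of 18 are unmeasured in one arm, and unmeasured infants differ from measured ones by g SD, the comparison shifts by (m/18) × g.

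- m = 1, g = 0.5: 0.03 SD
- m = 2, g = 1.0: 0.11 SD
- m = 3, g = 1.5: 0.25 SD

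Both m and g are assumed. The sign depends on the arm and on the direction of the gap. The shift is zero if loss and gap are equal by arm.

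**The case against.** **The source is unnamed, not shown to be wrong.** The chart mark for pregnancy outcomes and the infant release form suggest that the sponsor may already intend to use chart birth weight. This stands as a limit: if so, one sentence settles the matter. But Sections E and O define infant weight as staff-measured, and following them as written gives the measured-infants comparison.

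**Loss may be small.** The intensive-care rule needs both admission and critical illness, and eligibility excludes premature labor and preeclampsia. Section O provides home measurement, named contacts, reminder cards and admission searches, and Section F pays $100 for the visit. All of this stands. With 32 to 34 infants measured, the interval widens by only 3% to 7%, which is unlikely to change a conclusion in a pilot feasibility trial.

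**The chart may share the selection.** The release is reviewed at Study Visit 2, after randomisation, so women lost before then may lack both sources. This stands, and means that the remedy may reduce the problem without removing it.

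**Hospital weights are less standardised than a study scale.** This is fair, and is why the staff weight should be reported alongside. Step 3 shows how much extra error the chart could carry before it loses on precision.

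A reader might infer that the neonatal comparison is biased, or that intensive-care infants as a group are excluded. The documents support neither: they show no arm-dependent loss, and the exclusion is narrower than intensive-care admission.

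**Conclusion.** The point holds as a cheap improvement to the plan. As written, infant weight comes from an optional and restricted visit, and the available SAP text would compare measured infants only under an intention-to-treat label. A source that could cover more randomised women is within reach but is not named.

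The size is unknown. On assumed completion, the half-width runs from 0.68 SD with all 36 infants to 0.89 SD with 22, and the loss is slight if completion is high. The assumed bias range of 0.03 to 0.25 SD, in either direction, is an illustration and not an estimate; it can be zero.

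The conclusion rests on about 36 women randomised, equal arms, one weight per infant, chart coverage exceeding visit completion, and nothing in the unavailable SAP text that already names the source.

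**What to change.** In the SAP:

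- Abstract birth weight and gestational age at birth from the infant's medical record for every randomised woman whose record can be obtained, including intensive-care births and births outside the medical centre.
- Make chart birth weight by randomised arm, adjusted for GGI vs. GDM status, the infant-weight analysis on all available randomised participants.
- Report the staff-measured weight beside it.
- Label length, circumferences and skinfolds as the measured subset, and give the number unmeasured and the reasons by arm.

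I would not add adjustment for infant sex. It does not address missing weights, and allowing for chance imbalance at N = 36 it widens the interval by about 1.6% if sex explains no variance and 0.6% if it explains 2%. Nor would I test measured against unmeasured infants: with only a handful unmeasured, the test could neither show nor exclude selection.

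The cost is SAP wording and two chart fields. There are three possible limits: hospital weights are less standardised; coverage depends on the scope of the infant release, including whether it reaches other hospitals; and women lost before Study Visit 2 may still be missing. Chart weight does not replace the skinfolds, which address adiposity.
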